## 11.5 Appendix 5: Genetics

### Use and analysis of DNA

- Genetic variation may impact a participant's response to study medication, susceptibility to, and severity and progression of disease. Variable response to study medication may be due to genetic determinants that impact the mechanism of action of the drug; disease etiology; and/or molecular subtype of the disease being treated. Therefore, where local regulations and IRB/IEC allow, a blood sample will be collected for potential DNA analysis.
- DNA samples may be used for research related to UCB6114 and/or advanced solid tumors (locally recurrent or metastatic). They may also be used to develop tests/assays including diagnostic tests related to UCB6114 and/or interventions of this drug class and/or advanced solid tumors (locally recurrent or metastatic). Genetic research may consist of the analysis of one or more candidate genes or the analysis of genetic markers throughout the genome or analysis of the entire genome (as appropriate).
- DNA samples may be analyzed if it is hypothesized that this may help further understand the clinical data or help resolve issues with the clinical data; for example, PK outliers or potential safety observations.
- The samples may be analyzed as part of a multi-study assessment of genetic factors involved in the response to UCB6114 or study medications of this class to understand the participant's solid tumor or related conditions.
- The results of any genetic analyses will be reported separately.
- The Sponsor will store the DNA samples in a secure storage space with adequate measures to protect confidentiality.
- The samples will be retained while research on UCB6114 or study medications of this class continues, but no longer than 20 years (or other period according to local regulations).

## 11.6 Appendix 6: Rapid Alert Procedures

The aim of the Rapid Alert process is to stop the exposure to the study medication or concerned study procedure as soon as possible, following a confirmed or suspected safety issue, preventing its reoccurrence in other study participants as described in the Rapid Alert Team charter. Upon occurrence of an SAE and/or another safety event which may constitute a study/study part hold criterion, irrespective of its relationship with the study medication or the study conduct, the **investigator should notify the study Sponsor as soon as possible** (ideally within 2 hours of becoming aware of the event) by the following process:

1. A phone call to the study physician to alert them a safety event has been identified.
2. If the investigator is not able to reach the study physician, they should call the 24-hour rapid response helpline number. Upon receipt of a call from an investigator, the 24/7 helpline will contact a physician from UCB who will return the call to the investigator.
3. Additionally,
  - a. For UCB's RAVE® (ACQUIRE) study, complete the eCRF (S)AE page  
OR
  - b. For non UCB's RAVE (ACQUIRE) study or as back-up if UCB's RAVE® (ACQUIRE) is down, send a completed "Investigator (S)AE Report Form for Development Drug (For Rapid Alert Studies)" to the fax/email for Rapid Alert provided at the front of the protocol.

The form should include assessed seriousness, severity, and causality and should be filed in the Study Investigator's File.

Both the phone call and the completed form from the Investigator are crucial in assessing the safety of the study medication and in determining whether the event requires immediate action to place the study or individual study parts on hold and/or expedite reporting to the regulatory authorities. The (S)AE form should be completed in English and provided even if the data are incomplete, or if it is obvious that more data will be needed in order to draw any conclusions about the diagnosis or causality. Additional information (eg, laboratory reports) received by the investigator must be provided within 24 hours. All documents in the local language must be accompanied by a translation in English, or the relevant information included in the same document must be summarized in English in the (S)AE form.

During the call between the Investigator and the UCB physician the safety issue will be discussed to determine if there is sufficient evidence to declare a protocol hold criterion has been met for the entire study or for an individual study part. If the investigator and UCB physician agree a stopping criterion has not been met, dosing of the study may continue as per the study protocol and the discussion between the investigator and the UCB physician should be documented.

In all other circumstances, the investigator will be instructed to suspend dosing and the UCB physician will arrange an urgent, internal UCB Rapid Alert Team meeting. The Rapid Alert Team will review the information provided at the call along with the (S)AE form to determine whether or not a protocol hold criterion for the entire study or for an individual study part has been met. If it is determined that no criterion have been met, UCB will contact the investigator and inform them to recommence dosing. If it is determined a hold criterion has been met, UCB

will contact all investigators and notify them of the formal hold (please refer to Section [6.7](#) for further details).

If the investigator believes a protocol stopping criterion has been met for the entire study or for an individual study part, and they are unable to contact UCB prior to the next dose being due, they should postpone any further dosing until they have obtained feedback from UCB. In these circumstances dosing may be restarted if UCB and the investigator subsequently agree that no stopping criteria have been met.

This document cannot be used to support any marketing application and any extensions or variations thereof.  
PUBLIC COPY

## 11.7 Appendix 7: Country-specific Requirements

Not applicable.

## 11.8 Appendix 8: ECOG Performance Status Scale

ECOG Performance Status will be determined according to the following table:

Grade	ECOG performance status scale
0	Fully active, able to carry on all predisease performance without restriction
1	Restricted in physically strenuous activity but ambulatory and able to carry out work of a light or sedentary nature (eg, light housework, office work)
2	Ambulatory and capable of all selfcare but unable to carry out any work activities. Up and about more than 50% of waking hours
3	Capable of only limited self care, confined to bed or chair for more than 50% of waking hours
4	Completely disabled. Cannot carry on any selfcare. Totally confined to bed or chair
5	Dead

ECOG=Eastern Cooperative Oncology Group

## 11.9 Appendix 9: RECIST v1.1 guidelines

Guidelines here have been adapted from Eisenhauer, 2009.

### 11.9.1 Measurability of tumor at Baseline

At Baseline, tumor lesions/lymph nodes will be categorized measurable or nonmeasurable as follows:

#### Measurable Lesions

##### Tumor lesions (extra/non-nodal lesions)

Lesions that can be accurately measured in  $\geq 1$  dimension (longest diameter in the plane of measurement) with a minimum size of

- 10mm or greater when assessed by CT or MRI (slice thickness no greater than 5mm)
- 10mm or greater when assessed by caliper (lesions which cannot be accurately measured with calipers should be recorded as nonmeasurable)
- 20mm by chest X-ray

##### Malignant lymph nodes (nodal lesions)

Malignant lymph nodes with the short axis 15mm or greater when assessed by CT (CT slice thickness recommended to be no greater than 5mm)

NOTE: The shortest axis is used as the diameter for malignant lymph nodes, longest axis for all other measurable lesions.

## Nonmeasurable lesions

Nonmeasurable lesions will be considered as follows:

- All other lesions, including small lesions (extra/ non-nodal lesions) with longest diameter less than 10mm
- Malignant lymph nodes (nodal lesions) with  $\geq 10$  to  $< 15$ mm short axis
- Truly nonmeasurable lesions: such as pleural or pericardial effusions, ascites, inflammatory breast disease, leptomeningeal disease, lymphangitic involvement of skin or lung, clinical lesions that cannot be accurately measured with calipers, abdominal masses identified by physical exam that are not measurable by reproducible imaging techniques.

## Special considerations regarding lesion measurability

- Bone disease: Bone disease is nonmeasurable with the exception of soft tissue components that can be evaluated by CT or MRI and meet the definition of measurability at Baseline.
- Previous local treatment: A previously irradiated lesion (or lesion subjected to other local treatment) is non-measurable unless it has progressed since completion of treatment.

## Normal sites

- Cystic lesions: Simple cysts should not be considered as malignant lesions and should not be recorded either as target or non-target disease. Cystic lesions thought to represent cystic metastases can be measurable lesions, if they meet the specific definition above. If non-cystic lesions are also present in the same patient, these are preferred as target lesions.
- Normal nodes: Nodes with short axis  $< 10$  mm are considered normal and should not be recorded or followed either as measurable or non-measurable disease.

## Recording Tumor Assessments

All sites of disease must be assessed at Baseline. Baseline assessments should be done as close as possible to and prior to study start. For an adequate baseline assessment, all required scans must be done within 42 days prior to treatment and all disease must be documented appropriately. If a baseline assessment is inadequate, subsequent statuses generally should be indeterminate.

To assess objective response or future progression, overall tumor burden at Baseline should be estimated and compared to subsequent assessments.

## Baseline documentation of target lesions

All measurable lesions up to a maximum of 2 lesions per organ and 5 lesions in total and representative of all involved organs should be identified as target lesions at Baseline. Target lesions should be selected on the basis of size (longest lesions) and suitability for accurate repeated measurements. Record the longest diameter of each lesion, except in the case of pathological lymph nodes for which the short axis should be recorded. The sum of the diameters

(longest for non-nodal lesions, short axis for nodal lesions) for all target lesions at Baseline will be the basis for comparison to assessments performed during the study.

- If two target lesions coalesce, the measurement of the coalesced mass is used. If a large target lesion splits, the sum of the parts is used.
- Measurements for target lesions that become small should continue to be recorded. If a target lesion becomes too small to measure, 0 mm should be recorded if the lesion is considered to have disappeared; otherwise a default value of 5 mm should be recorded.

NOTE: When nodal lesions decrease to <10 mm (normal), the actual measurement should still be recorded.

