#### Type of participant and disease characteristics

2. Participant has histologically and/or cytologically confirmed diagnosis of one of the following advanced solid tumor types: colorectal adenocarcinoma, gastric adenocarcinoma, adenocarcinoma of the gastroesophageal junction, or pancreatic cancer.
3. Participant has advanced disease (ie, unresectable locally recurrent or metastatic).
4. Participant must have received and is refractory or intolerant to standard therapy appropriate for the tumor type.

---

5. Participant has measurable or non-measurable disease as defined by the relevant RECIST (Appendix 9, Section 11.9).
6. Participant has a performance status of  $\leq 1$  on the Eastern Cooperative Oncology Group (ECOG) scale (Appendix 8, Section 11.8).
7. Participant must have tumor lesion(s) or metastases amenable to biopsy, excluding bone metastases, as confirmed by a radiologist, if appropriate, and as deemed safe by the Investigator.
8. Participant must consent to the mandatory pretreatment and on-treatment tumor biopsies.
9. Participant has discontinued all previous therapies for cancer (with exception of treatments defined in Section 6.5.2), including chemotherapy, radiotherapy, cancer-related hormonal therapy, or other investigational therapy for a minimum of 28 days or 5 half-lives (whichever is shorter) (6 weeks for mitomycin-C or nitrosoureas) prior to start of study medication and recovered from the acute effects of therapy.
10. Any clinically significant treatment-related toxicity from prior therapy must have resolved to Grade  $\leq 1$  prior to study entry, with the exception of alopecia.
11. Participant has an estimated life expectancy of  $\geq 12$  weeks.

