### **Biopsy procedure in Part A1**

The most suitable lesion(s) to be biopsied should be discussed between the oncologist, radiologist, and/or colleague performing biopsy of cutaneous metastases or endoscopic biopsy, as appropriate.

Tumor biopsies are mandatory, however biopsies are to be performed, and the potentially required local anesthesia administered, only if considered to be of low risk to the participant, as determined by the Investigator and the health care professional performing the biopsy.

It is preferred that up to 5 cores per biopsy, 18-gauge in diameter and  $\geq 1$  cm in length will be obtained during each procedure, if considered safe and feasible. A single baseline biopsy core transferred to neutral buffered formalin (NBF) will constitute a successful biopsy. If an initial attempt at a biopsy is unsuccessful, the patient will be given an option to proceed with a repeated attempt. If the baseline biopsy remains unsuccessful no further biopsies will be performed but the patient may remain on the study and receive study medication.

If the study participant chooses not to undergo biopsies subsequent to the baseline biopsy, he/she will be withdrawn from the study. Feasibility for the subsequent biopsies will be assessed by the Investigator/the health care professional performing the biopsy and should include a consideration of patient safety. If the subsequent biopsy is deemed to be unsafe and/or not feasible, the study participant may remain on study and receive study medication.

The lesion from which each biopsy is taken will be documented in the Tissue Acquisition Form, and, if possible, an attempt will be made to collect the on-treatment biopsies from the same lesion as the Baseline biopsy.

The use of imaging to facilitate biopsies will be decided by members of the Interventional Radiology team and may include ultrasound, CT scan, or MRI. Should a CT scan be needed for biopsy, the number of scans for each procedure will be limited to the minimum number and duration required to safely obtain the biopsy.

Instructions pertaining to sample collection, processing, storage, labeling, and shipping are provided in the biopsy manual for this study.

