### **Baseline documentation of nontarget lesions**

All nonmeasurable disease is nontarget. All measurable lesions not identified as target lesions are also included as non-target disease. Measurements are not required but rather assessments will be expressed as ABSENT, INDETERMINATE (not evaluable), PRESENT/NOT INCREASED (present), INCREASED (unequivocal progression). Multiple non-target lesions in one organ may be recorded as a single item on the eCRF (eg, 'multiple enlarged pelvic lymph nodes' or 'multiple liver metastases').

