#### **Target lesions**

- Complete Response (CR): Complete disappearance of all target lesions with the exception of nodal disease. All target nodes must decrease to normal size (short axis <10 mm). All target lesions must be assessed.
- Partial Response (PR): Greater than or equal to 30% decrease under Baseline of the sum of diameters of all target measurable lesions. The short diameter is used in the sum for target nodes, while the longest diameter is used in the sum for all other target lesions. All target lesions must be assessed.
- Stable: Does not qualify for CR, PR or Progression. All target lesions must be assessed. Stable can follow PR only in the rare case that the sum increases by <20% from the nadir, but enough that a previously documented 30% decrease no longer holds.
- Progressive disease: 20% increase in the sum of diameters of target measurable lesions above the smallest sum observed (over Baseline if no decrease in the sum is observed during therapy), with a minimum absolute increase of 5 mm.
- Indeterminate. Progression has not been documented, and one or more target measurable lesions have not been assessed; or assessment methods used were inconsistent with those used at Baseline; or one or more target lesions cannot be measured accurately (eg, poorly

---

visible unless due to being too small to measure); or one or more target lesions were excised or irradiated and have not reappeared or increased.

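### In Part A1 the target-lesion rule can put the biopsied lesion into the RECIST sum of diameters: low severity, cheap to close

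*Protocol*

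**What the plan says.** **Target lesions (Protocol, Section 11.9.1).** The targets are "All measurable lesions up to a maximum of 2 lesions per organ and 5 lesions in total and representative of all involved organs". The next sentence adds that "Target lesions should be selected on the basis of size (longest lesions) and suitability for accurate repeated measurements". Whatever is left over goes to the non-target group: "All measurable lesions not identified as target lesions are also included as non-target disease".

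**Biopsies (Section 5.1.2, Section 9.8.7 and its Part A1 procedure).** An inclusion criterion reads "Participant must consent to the mandatory pretreatment and on-treatment tumor biopsies". On technique, "It is preferred that up to 5 cores per biopsy, 18-gauge in diameter", with a length of at least 1 cm. On the choice of lesion, "The most suitable lesion(s) to be biopsied should be discussed between the oncologist, radiologist, and/or colleague performing biopsy". For the second sample, where possible, "an attempt will be made to collect the on-treatment biopsies from the same lesion as the Baseline biopsy". None of this text mentions target or non-target status.

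**Removed lesions (Section 11.9.2).** The target response is Indeterminate, provided progression has not been documented, when "one or more target lesions were excised or irradiated and have not reappeared or increased".

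**Timing (Tables 1-5 and 1-6).** The screening scan may be up to 42 days before dosing and the baseline biopsy falls between Day -28 and Day -1. The on-treatment biopsy is placed, whenever possible, between Cycle 1 Day 15 and Cycle 2 Day 1 (Cohorts 1, 2 and 4) or between Cycle 2 Day 1 and Cycle 2 Day 15 (Cohort 3). Scans follow every 8 weeks from Day 1, with a window of 7 days either way.

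**The concern.** A lesion cored at baseline and again on treatment may swell, bleed or scar. If it also contributes to the sum of diameters, a change in its size is attributed to the tumor's behavior under UCB6114, and the recorded response mixes procedure with drug.

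Three uses of the data are touched:
- ORR, DCR and PFS in Part A1 are exploratory, but Section 3 counts antitumor activity in the totality of data from which the recommended dose is determined.
- Section 10.3.3.3 relates pharmacodynamic variables, including those from tumor samples, to tumor response. A single cored lesion could supply both sides of that comparison.
- Under Section 7.1.3, progression after Cycle 1 normally ends study medication. A false increase could therefore alter exposure and PFS, not only a response table.

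Target status is fixed at baseline, so an overlap that nobody recorded is hard to repair at analysis.

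**Working it through.** The plan states no figure for this point, so there is none to reproduce. The check has four steps.

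**1. When is the biopsied lesion forced into the sum?** Below the cap of 2 per organ and 5 in total, Section 11.9.1 takes all measurable lesions. The wording on size and suitability has room to choose only when there are more lesions than the cap allows. So a biopsied lesion must be a target if (a) it is measurable and (b) the participant is at or below the cap. Part A1 also admits participants with non-measurable disease only (Section 5.1.2, criterion 5), so (a) need not hold.

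**2. Do the biopsies lie between the two scans?**
- Eligibility must be confirmed before the biopsy (footnote b of Tables 1-5 and 1-6; Section 9.8.7). It covers RECIST disease status and the presence of a lesion fit for biopsy. The baseline scan therefore normally comes first, although no text fixes that order.
- First response scan: 8 weeks from Day 1 is Day 57, so Days 50 to 64.
- Cohorts 1, 2 and 4, second biopsy on Days 15 to 29: 50 − 29 = 21 days to 64 − 15 = 49 days before the scan.
- Cohort 3 (21-day cycles), second biopsy on Days 22 to 36: 50 − 36 = 14 days to 64 − 22 = 42 days before the scan.

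If the windows are kept, the first response scan follows both biopsies.

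**3. What change would alter a response category?** Section 11.9.2 sets progression at a 20% rise with at least 5 mm, and partial response at a 30% fall.
- One 20 mm target: 20% is 4 mm, so the 5 mm minimum governs progression. Partial response needs 0.30 × 20 = 6 mm.
- Two 20 mm targets (sum 40 mm): progression needs 8 mm and partial response 12 mm, if all the change is in the sampled lesion.

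**4. How much can coring itself remove?** Assumptions, not in the documents: a spherical lesion of diameter D, cores 10 mm long and 0.8 to 1.27 mm wide (c), k = 5 to 10 cores over the two procedures, and no bleeding, swelling or scarring. Fraction of volume removed = k(π/4)c²·10 ÷ (πD³/6). Fall in diameter = 1 − (1 − fraction)^(1/3).

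| Lesion | Volume removed | Fall in diameter |
|---|---|---|
| 10 mm | 4.8% to 24.2% | 1.6% to 8.8% |
| 20 mm | 0.6% to 3.0% | 0.2% to 1.0% |

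In millimeters the worst cases are 0.088 × 10 = 0.88 mm and 0.01 × 20 = 0.2 mm. For a sole target, partial response needs 3 mm and 6 mm respectively. Tissue loss from coring does not come near a threshold. What remains is swelling, bleeding and scarring, which the documents do not allow anyone to size.

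**Weight of one participant.** 1/8 = 12.5 percentage points of a cohort's ORR or DCR; 1/32 = 3.1 points over the whole of Part A1.

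**The case against.** The case for leaving the text alone has real force.

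- *Not every participant is affected.* A reader might infer that all of the up to 32 participants have a biopsied target. The documents do not support that. The sampled lesion may be non-measurable, a participant above the cap may have other lesions chosen, and resampling the same lesion is only attempted. An unsuccessful baseline biopsy ends sampling, and an unsafe or infeasible second one can be omitted. This stands: the affected subset is unknown.
- *Excision is not planned.* A reader might infer that biopsy will make later responses Indeterminate. The protocol describes 18-gauge cores, and its mention of cutaneous and endoscopic biopsy does not say that a lesion is removed. The Indeterminate rule also stops a removed lesion from being scored as a response. This stands: that outcome arises only if a small target is in effect taken out and progression is not documented.
- *Responses are confirmed.* Sections 9.6.1 and 10.4.1.1 require a second scan at least 4 weeks later, so a transient shrinkage would not count as CR or PR. This stands for responses. Progression has no such confirmation; Section 7.1.3 allows continued treatment with reimaging only where progression is unclear and the participant may be benefiting.
- *The endpoints are exploratory.* Section 10.2 rules out formal testing in Part A1, the stopping rule for a schedule rests on DLTs, and all four cohorts carry the same biopsy requirement with similar gaps to the scan. Little distortion between schedules is expected. This stands and keeps the severity low.

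The clause on suitability for repeated measurement does not answer the point: it does not mention biopsy, and at or below the cap all measurable lesions are targets.

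**Conclusion.** The concern holds in a limited form. For a Part A1 participant at or below the cap whose biopsied lesion is measurable, the protocol places that lesion in the sum of diameters and normally has it cored between the baseline scan and the first response scan. Procedure effects can then enter ORR, DCR and PFS and, with least protection, the progression call.

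The size cannot be stated. Up to 32 participants are exposed to the biopsies, the number with a biopsied target is unknown, and the frequency and extent of swelling, bleeding or scarring are not given. The small effect of coring alone rests on the assumed geometry in the check. The timing rests on the windows in Tables 1-5 and 1-6 being kept and on the baseline scan preceding the biopsy, which the eligibility step implies but no sentence requires.

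This is a cheap improvement of low severity. It is not a flaw that undermines Part A1.

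**What to change.** Add to Sections 11.9.1 and 9.8.7, for Part A1:

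- The lesion chosen for biopsy is named before target lesions are recorded, and is recorded as non-target when at least one other measurable lesion exists.
- If it is the only measurable lesion, it stays a target and is flagged in the data, and the baseline scan precedes the baseline biopsy.
- ORR, DCR and PFS are repeated without flagged participants. The detail of this repeat can sit in the module's SAP.

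The cost is a short addition in two sections and one data flag, with no extra scan or procedure. The Tissue Acquisition Form already identifies the sampled lesion, and Appendix 9 already has a special rule for lesions with previous local treatment. There are two drawbacks: some participants will have one target lesion fewer, and a biopsied non-target lesion can still yield progression through an unequivocal increase, so the artefact is reduced but not removed.
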